For clinic staff, documentation of informed consent will be waived. No HIPAA authorization will be collected, as no protected health information is being collected by clinicians. At the beginning of each interview, the interviewer will capture consent on the audio recording device. Interviews will last approximately 30 minutes, and will consist of questions derived from the Consolidated Framework for Implementation Research (CFIR; Damschroder et al., 2009). Questions will center on the following CFIR constructs: intervention characteristics, outer setting, and inner setting. Based on the first interview transcript, a codebook will be developed under the following categories: evidence strength and quality, relative advantage, adaptability, complexity, patient needs and resources, structural characteristics, tension for change, and compatibility. Once the final codebook is established, interview transcripts will be dually coded by the PI and another study staff member, with coding discrepancies resolved by consensus.

QUANTITATIVE PROCEDURES. The study team will receive a dataset from Duke University Health System, where [name] will collect data from Amazon Mechanical Turk (MTURK; <https://www.mturk.com>). Data from MTurk will be collected by the Duke team via an anonymous survey hosted by Duke Qualtrics. Data will be moved to VA from Duke in accordance via a VA-owned thumbdrive. All data will be de-identified, such that the study team will neither collect nor retain any PII or PHI. Data will include: HIV, smoking, and veteran status; demographic information (age; race; ethnicity; relationship status; sexual orientation; gender identity; U.S. state/territory; education; income; VHA patient status); and for HIV-positive participants only, age at HIV diagnosis, last CD4 count, and last viral load). Data will also include participants' ratings of satisfaction with 148 relapse prevention text messages used in the SmokefreeVET library, as well as additional messages developed by the Duke research team.

AIM 2 METHODS

To identify potential treatment moderators and further understand current health services for smoking cessation among Veterans living with HIV, it is essential to determine existing health disparities in cessation treatment among VHA patients with and without HIV.

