Quantitative Analysis. Regarding quantitative data received from Duke, data from veterans who smoke, people living with HIV who smoke, and members of the general public who smoke will be analyzed separately. First, data will be cleaned. Participants will be excluded from analysis if they meet any of the following criteria: greater than 2 endorsed bogus items, self-reported “very little” or “no” effort or attention, or a “no” response to the question “In your honest opinion, should we use your data in our analyses in this study?” After data cleaning, the following descriptive statistics will be calculated for satisfaction ratings on each SmokefreeVET message: range, mean, and standard deviation. Items falling below an 8 on mean satisfaction will be reviewed by the study staff in the context of qualitative findings to make final decisions regarding their inclusion in the final relapse-prevention message library.

Aim 2:

In order to examine disparities in healthcare delivery of smoking cessation prescriptions, we will use a longitudinal retrospective design. Generalized linear mixed modeling (GLMM) with a logit link and binomial variance will be used to determine differences by age, race, ethnicity, HIV, Hepatitis C, psychiatric disorder, and severe average pain in likelihood of pharmacotherapy dispensation during a given year. GLMMs appropriately accommodate multi-level data structures with unbalanced design for analyzing repeated observations across multiple individuals nested within clinics. Clinic- and person-level random effects will be included in statistical models to account for correlation among patients within the same clinic and repeated measurements on the same individual over time, respectively. Covariates will be assessed for collinearity before entering them simultaneously into the GLMM.

Aim 3:

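### Aim 1b takes HIV status from anonymous self-report, and its cleaning rules test response quality but not group membership

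*Combined protocol and SAP*

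**What the plan says.** The Quantitative Procedures under AIM 1 METHODS describe the source: "Data from MTurk will be collected by the Duke team via an anonymous survey hosted by Duke Qualtrics". The dataset then passes to the VA team without identifiers: "All data will be de-identified, such that the study team will neither collect nor retain any PII or PHI". Group status is one of the survey fields: "Data will include: HIV, smoking, and veteran status". The dataset also holds age, VHA patient status and, "for HIV-positive participants only, age at HIV diagnosis, last CD4 count, and last viral load".

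The Quantitative Analysis paragraph for Aim 1 under DATA ANALYSES splits respondents by that status: "data from veterans who smoke, people living with HIV who smoke, and members of the general public who smoke will be analyzed separately". Cleaning comes first and has three exclusions:

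- The opening rule reads "Participants will be excluded from analysis if they meet any of the following criteria: greater than 2 endorsed bogus items".
- The second removes respondents who rate their own effort or attention as very little or none.
- The third removes those who answer no to "In your honest opinion, should we use your data in our analyses in this study".

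Messages with mean satisfaction under 8 then go to study staff, who decide on them together with the qualitative findings.

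**The concern.** Answers to the survey's own questions decide who is counted as a smoker living with HIV. With no identifiers kept, the VA team cannot compare those answers with a record. The three exclusions ask whether someone answered with care and in good faith. A careful respondent who wrongly reports HIV can pass all of them. The age, diagnosis, CD4 and viral load fields would allow at least a coherence check, but no rule uses them.

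Other aims lean less on a bare claim. The Aim 1a interview patients are identified from VA records, Aim 2 uses diagnosis codes, and Aim 3 supports clinic referral with chart review.

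At stake is which messages get a second look for a library meant for Veterans living with HIV. A mean under 8 prompts review, but a message whose mean is lifted to 8 or above by people outside the group does not reach review through that mean. The results would also be described as the views of smokers living with HIV, with nothing in the plan to support that label.

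**Working it through.** The documents give no sample size, false-claim rate or expected HIV share for Aim 1b, so there is no stated figure to reproduce. The check asks how far the answer depends on what is missing.

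**Formula.** Let p be the true share with HIV among responding smokers, r the share of HIV-negative respondents who claim HIV, and k the share of those claimants who pass the cleaning rules. If all true members are kept, the false share of the HIV group is

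F = (1 − p)·r·k / [(1 − p)·r·k + p].

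**Inputs.** The Background gives over 1 million people with HIV in the U.S., and smoking rates of about 40% with HIV and 20% in general. The population size is an assumption.

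- With 330 million people, HIV prevalence is about 0.3%, and p = 0.003 × 0.4 / (0.003 × 0.4 + 0.997 × 0.2) = 0.598%, or about 0.6%.
- With 200 to 260 million adults, p ≈ (0.4 × 1 million) / (0.2 × adults) = 1.0% to 0.77%.

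Both describe recruitment that does not target HIV. Targeting would raise p, so 5% and 10% are shown as well. Every value of r is assumed.

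**False share F with k = 1:**

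| p | r = 0.5% | r = 1% | r = 2% | r = 5% |
|---|---|---|---|---|
| 0.6% | 45% | 62% | 77% | 89% |
| 0.8% | 38% | 55% | 71% | 86% |
| 5% | 9% | 16% | 28% | 49% |
| 10% | 4% | 8% | 15% | 31% |

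Two cells in full, at r = 1%:

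- p = 0.6%: 0.994 × 0.01 / (0.994 × 0.01 + 0.006) = 0.00994 / 0.01594 = 62%.
- p = 10%: 0.9 × 0.01 / (0.9 × 0.01 + 0.1) = 0.009 / 0.109 = 8%.

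If the existing rules removed half of the false claimants (k = 0.5), these would be 0.00497 / 0.01097 = 45% and 0.0045 / 0.1045 = 4%.

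**Effect on the cut-off (illustrative means).** If true members rate a message 7.5 and false claimants 8.5, the observed mean is 7.5 + F. It reaches 8 at F = 50%. At F = 62% it is 8.12 and the message is not flagged; at F = 8% it is 7.58 and still flagged. With the ratings reversed, the mean is 8.5 − F. At F = 62% it is 7.88, and the only result is an unneeded review.

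**The case against.** The strongest objection is that the size is all assumption. At p = 0.598%, finding 100 true members would take about 100 / 0.00598 ≈ 16,700 responding smokers. Aim 1b names smokers living with HIV as a group to be studied, so recruitment with no targeting is doubtful. The partner university runs the survey, and its screener and recruitment procedures are not described here, so eligibility may be checked before the VA team receives the data. This stands. It is why no single false share can be quoted, although targeting could also raise the false-claim rate.

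The consequence is limited too. Aim 1b is descriptive. A low mean prompts review and does not remove a message. The reviewers have interviews with record-identified HIV-positive patients, and text content can be revised after each Aim 3 cohort. Status from the survey plays no part in Aim 2 or Aim 3. This also stands, with one gap: the interviews use examples of each type of message and are not described as covering all 148, so for some messages the survey mean may be the only item-level signal.

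The available fields are themselves self-report. Checks on them catch incoherent answers, not a claimant who gives plausible ones. This is correct and limits what the remedy can do.

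A reader might also infer that the present rules catch only careless respondents. The documents do not support this: the content of the bogus items is not given, and the question on use of the data could lead a false claimant to withdraw.

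**Conclusion.** The gap is real and modest. HIV status in Aim 1b is anonymous and unverified, it alone defines the group, and no listed exclusion tests it. Some ratings reported for smokers living with HIV may come from people without HIV.

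The size is unknown. At an assumed 1% false-claim rate, with every false claimant passing the rules, the false share runs from about 62% (0.6% truly with HIV) to about 8% (10% truly with HIV). Neither end can be chosen from the documents.

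Two stronger readings are not supported. One is that false claimants make up much of the group, which needs both a false-claim rate and untargeted recruitment that the documents do not state. The other is that the survey means settle which messages stay, when they only decide which are sent for review. A cheap change to the cleaning rules is still worthwhile, because an inflated mean can keep a message from that review.

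**What to change.** Add the following to the Aim 1 Quantitative Analysis cleaning rules, to be applied before group means are computed:

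1. Remove from the HIV group any respondent whose age at HIV diagnosis exceeds current age, or whose CD4 count or viral load entry is impossible. Define impossible in advance, for the response format the survey used.
2. Report the number removed.
3. Show whether each message falls below 8 with and without respondents who leave all three HIV detail fields blank. Send to review any message below 8 in either version.
4. State that HIV and veteran status are self-reported, and that these checks do not detect a false claimant who gives plausible answers.

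Do not add a parallel rule that treats veteran and VHA-patient answers as conflicting. A veteran who is not a VHA patient is no contradiction, and such a rule would remove genuine veterans. A VHA patient who reports not being a veteran is already outside the veteran group.

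The cost is a few lines of code on fields already received, a slightly smaller HIV group, and the loss of a few genuine members who mistype a value.
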